4.2.2 Estimated Time Needed to Enroll Subject Population

Enrollment in this study is expected to take approximately 2 to 3 years, depending on the rate of site activation and enrollments.

4.3 Objectives

4.3.1 Primary Objective

The primary objective of this study is to characterize the image quality, clinical impact, and diagnostic utility of MRI in patients undergoing clinically indicated, non-thoracic MRI scans who are implanted with a St. Jude Medical pacemaker, ICD, or CRT device.

4.4 Endpoints

4.4.1 Primary Endpoints

4.4.1.1 Primary Endpoint #1:

The proportion of MRI scans from pacemakers or CRT-Ps providing sufficient image quality to allow for a diagnostic interpretation.

4.4.1.2 Primary Endpoint #2:

The proportion of MRI scans from ICDs or CRT-Ds providing sufficient image quality to allow for a diagnostic interpretation.

4.4.2 Additional Data

- Demographics: gender, age, ethnicity, race, cardiac disease history, arrhythmia history, etc.
- A summary of scan location (i.e. head, extremity, and lumbar).
- A summary of clinical findings based on review of MRI scans
- A summary of device electrical measurements at the MRI Scan Visit (before and immediately after the MRI scan) and at Follow-up Visit(s).
- A summary of adverse events (ADE, SADE, UADE)
- A summary of MRI-related complications
- Mortality
- Estimate of the incidence rate of device patients undergoing a clinically indicated MRI.

The above data will be summarized by each main device group (pacemaker/CRT-P and ICD/CRT-D).

Clinical Investigational Plan

4.5 Subject Selection

A patient, who meets all of the inclusion criteria, and none of the exclusion criteria, is eligible to participate in this study.

4.5.1 Inclusion Criteria

*Eligible patients will meet **all** of the following:*

1. Patient is implanted with a market-released St. Jude Medical pacemaker, ICD, or **CRT current generation** device listed in the study protocol and any market-released pacing or defibrillation lead.
2. Patient's device and all leads must be implanted for at least 6 weeks prior to the scheduled date of the MRI.
3. Patient has a clinical indication for a non-thoracic MRI scan, where MRI is the imaging modality of choice that will give adequate results to manage the patient.
4. Patient is scheduled for a non-thoracic MRI scan up to 1.5T.
5. Patient has a pacemaker, ICD, or CRT device implanted pectorally.
6. Patient has the ability to provide informed consent for study participation and be willing and able to comply with the study procedures.
7. Patient is 18 years or above, or of legal age to give informed consent specific to state and national law.

4.5.2 Exclusion Criteria

*Subjects are **not** eligible for clinical study participation if they meet **any** of the following exclusion criteria:*

1. Patient has an ICD/CRT-D and is pacemaker dependent
2. Capture threshold is greater than 2.5 volts at 0.5 ms for RA and RV leads
3. Pacing lead impedance is NOT within range (i.e. ≥ 200 and ≤ 2000 ohms)
4. High voltage lead impedance (HVLI) is NOT within range (i.e. ≥ 20 and ≤ 200 ohms)
5. Patient has a device generator battery voltage at elective replacement interval (ERI)
6. Patient has another existing active implanted medical device (e.g. neurostimulator, infusion pump, etc.) that has MR labeling that will not allow the MRI scans to be completed.
7. Patient has other non-MRI compatible device or material implanted

NOTE:

- MRI compatible knee replacements, hip replacements, stents, etc. may be included as long as the labeling of these devices allow MRI scans conducted per this protocol

Clinical Investigational Plan

- MRI compatible mechanical, prosthetic, and bioprosthetic heart valves may be included as long as the labeling of these devices allow for MRI scans conducted per this protocol
- Non-removable dental implants may be included
- 8. Patient has a lead extender, adaptor, or capped/abandoned lead
- 9. Patient is pregnant

4.6 Subject Population

4.6.1 Patient Screening

All patients presenting at the investigational site may be screened by a member of the investigational team who has been trained on the CIP and delegated to do so.

Patients who do not meet the inclusion/exclusion criteria will not be eligible to participate in this study.

Patients meeting the inclusion/exclusion criteria will be fully informed about the study and asked to review and sign informed consent. If the subject agrees, a duly signed and dated Patient Informed Consent will be obtained.

4.6.2 Point of Enrollment

Subjects are considered enrolled after the informed consent form has been signed (Refer to section 4.7 for the Informed Consent Process), it has been verified that the subject meets all of the inclusion and none of the exclusion criteria, and the subject's device is programmed to enter the MRI environment.

4.6.3 Enrollment of Medicare Beneficiaries

This clinical study will enroll Medicare beneficiaries and therefore conforms to all standards of Medicare coverage requirements. Section 3.0 describes how all enrolled subjects, including Medicare beneficiaries, may be affected by the device under investigation. Subjects enrolled in the clinical study are expected to be consistent with the Medicare population based on age and as such the study results are expected to be generalizable to the Medicare population.

4.6.4 Vulnerable Population

This clinical study will be conducted in a vulnerable population only when the study cannot be carried out in non-vulnerable populations. At the current time, this study does not allow, and will not include vulnerable patients for enrollment into the study.

Clinical Investigational Plan

4.7 Informed Consent Process

4.7.1 General Process

Prior to enrolling in the clinical study and conducting study-specific procedures, all subjects will be consented, as required by applicable regulations and the center's IRB. Informed consent must be obtained from each subject prior to any study related procedures. Each consent form must be signed and dated by the subject and by the person obtaining the consent.

The principal investigator or his/her authorized designee will conduct the Informed Consent Process. This process will include a verbal discussion with the subject on all aspects of the clinical study that are relevant to the subject's decision to participate in the clinical study.

The subject shall be provided with the informed consent form that is written in a language that is understandable to the subject and has been approved by the center's IRB. Failure to obtain informed consent from a subject prior to study enrollment should be reported to St. Jude Medical within 5 working days and to the reviewing center's IRB/ consistent with the center's IRB reporting requirements.

5.0 Devices Under Investigation

5.1 Device Descriptions

This study includes any of the following market-released St. Jude Medical pacemaker, ICD, or CRT current generation devices and any market-released pacing or defibrillation lead that were previously implanted in patients with a clinical indication for the device system prior to participation in this study. Subjects with devices in the following families are eligible to enroll (See Table 3):

Table 3. List of Eligible Devices by Type and Family

Device Type	Device Family
Pacemakers	Assurity™ and Assurity MRI™
	Endurity™ and Endurity MRI™
ICDs	Ellipse™
	Fortify Assura™
CRTs	Allure™/Allure Quadra™ /Allure Quadra MP™ CRT-P
	Quadra Assura™/ Quadra Assura MP™ CRT-D

The SJM pacemaker, ICD, and CRT devices are supported by the St. Jude Medical Merlin Patient Care System (Merlin PCS) programmer.

[figure not shown]
Abbott

Study Document No: SJM-CIP-10130 Ver. D
Study Name: SJM MRI Diagnostic Imaging Registry

Clinical Investigational Plan

5.2 Device Handling & Storage

Instructions for use, storage and handling instructions, preparation for use and any precautions can be found in the User's Manuals for each the market-released devices and leads.

**Clinical Investigational Plan****6.0 Procedures****6.1 Study Flow Chart****Figure 1: Study Flow Chart**

**Clinical Investigational Plan****6.2 Procedures**

The study will be conducted in accordance with the CIP. All parties participating in the conduct of the study will be qualified by education, training, or experience to perform their tasks and this training will be documented appropriately.

The study will not commence until St. Jude Medical receives written approval from the IRB and relevant regulatory authorities and all required documents have been collected from the site(s).

All required study procedures at each specified interval are outlined in the section below. Refer to Table 4.

Table 4: Study Procedures and Data Collection

Procedure/Evaluation	Study Schedule			Follow-Up Visit(s) 2-12 days and/or 1 Month (-7/+ 14 days) Post MRI Scan*	
	MRI Scan Visit		Post-MRI (Same day as MRI Scan)		
	Pre- MRI	During MRI			
Informed Consent & Inclusion/Exclusion Evaluation	✓				
Medical and Surgical History	✓				
Demographic Information	✓				
Implanted SJM pacemaker, ICD, or CRT device system info.	✓				
Complete the SJM provided MRI Hazard Checklist or a site-specific checklist, per site's standard of care	✓				
Obtain device measurements (remaining battery capacity, capture threshold, sense, pacing and HVLI impedances, as applicable) at permanently programmed settings	✓		✓	✓	
Program the appropriate device settings before MRI	✓				
Monitor subject with ECG along with the site's routine monitoring**		✓			
Assess subject for adverse events		✓	✓	✓	
Program device to original settings after MRI scan			✓		
Clinical Evaluation of MRI scan			✓		
Report deviations and withdrawal	✓	✓	✓	✓	

*Refer to the study flow chart for follow-up schedule

** In cases where ECG monitoring is not readily available, monitoring via pulse oximetry alone is considered acceptable

Clinical Investigational Plan

6.3 Pre-MRI Scan Procedures

6.3.1 Informed Consent & Inclusion/Exclusion Evaluation

The principal or delegated study personnel are responsible for screening all potential subjects to determine subject eligibility for the study as outlined in the inclusion and exclusion criteria and obtaining informed consent, as outlined in section 4.7.

6.3.1.1 Situations where subject does not meet eligibility criteria

If a subject does not meet all inclusion criteria or meets any of the exclusion criteria, the subject cannot participate in the study and cannot be enrolled. In case the subject was already consented to participate in the study, but does not meet inclusion/exclusion criteria, the following actions will be taken.

Issues where patient was consented, but did not meet inclusion/exclusion criteria	Action
If the subject's device was NOT programmed to enter the MRI environment and the MRI Scan did NOT take place (i.e. subject changed their mind about undergoing MRI scan)	
• Document enrollment information (name of the study, date of consent and inclusion/exclusion) in the subject's medical and/or study records• Complete the Enrollment CRF and Screen Failure/Withdrawal CRF. The subject is a screen failure.
If the subject's device WAS programmed to enter the MRI environment but the MRI Scan did NOT take place (i.e. subject changed their mind about undergoing the MRI scan):	
• Document enrollment information (name of the study, date of consent and inclusion/exclusion) and MRI Scan Visit information in the subject's medical and/or study records• Complete the Enrollment CRF• Complete the Deviation CRF for inclusion/exclusion criteria not met• Complete the Withdrawal CRF. The patient is withdrawn
If the subject's device WAS programmed to enter the MRI environment AND the MRI Scan has been performed:	
• Document enrollment information (name of the study, date of consent and inclusion/exclusion) and MRI Scan Visit information in the subject's medical and/or study records• Complete the Enrollment CRF• Complete the MRI Scan CRF• Complete the Deviation CRF for inclusion/exclusion criteria not met

Clinical Investigational Plan

6.3.2 Baseline Data Collection

Collect data on the subject including demographics, medical/surgical history, and St. Jude Medical device system information

6.3.3 Clearing the Subject for the MRI Scan

The radiologist or designated radiological staff member must determine the subject's eligibility for an MRI scan prior to the MRI scan (per standard of practice).

The study **MRI Hazard Checklist** may be used to document a radiologist or designated member of the radiology department has cleared the subject for an MRI scan. Alternatively, the radiology department may use its own hazard checklist in lieu of the study MRI Hazard Checklist. This documentation should be maintained with the subject's medical and/or study records.

In order to safely perform an MRI scan on a subject with a St. Jude Medical device system, the physician/clinician should follow the recommended guidelines below:

- Review the potential adverse events in an MRI environment in Table 1.
- Generate a report of the patient's permanently programmed parameters
- Perform device assessment
- Program recommended settings for the MRI environment
- Subject receives the MRI Scan
- Reprogram device to patient's permanently programmed parameters

6.3.5 Pre-MRI Device Programming

Program the subject's device per physician discretion. Recommended settings for the MRI environment are provided below in Table 5.

Table 5. Recommended Device Settings for the MRI Environment

Parameters	Pacemaker/CRT-P with stable underlying rhythm	Pacemaker/CRT-P and dependent	ICD/CRT-D with stable underlying rhythm
Pacing Mode*	Pacing Off	VOO/DOO	Pacing off
MRI Base Rate	n/a	Per physician	n/a
MRI Paced AV delay	n/a	Per physician	n/a
MRI Pulse Amplitude	n/a	5.0 V, 7.5 V**	n/a
MRI Pulse Width	n/a	1.0 ms**	n/a
MRI Pulse Configuration	n/a	Bipolar	n/a
MRI V Pacing Chamber***	n/a	RV only	n/a
Tachy Therapy	n/a	n/a	Disabled

***Note:** Determine whether or not the subject requires pacing support during the MRI scan. When pacing support is needed, program the asynchronous pacing mode (VOO). When pacing support is not needed, program the Pacing Off.

****Note:** Not suggested for LV lead in CRT-P device. Turn magnet mode off if applicable

***** Note:** Only applicable in CRT devices.

Some subjects may be susceptible to cardiac arrhythmia induced by competitive pacing when an asynchronous MRI Mode is selected. For these subjects, it is important to select an appropriate MRI pacing rate and AV delay to avoid competitive pacing and then minimize the duration of the asynchronous pacing operation.

Clinical Investigational Plan

6.3.6 Setting up ECG and/or Pulse Oximetry

Set up the ECG and/or pulse oximetry to monitor heart rate. Place the oximetry clip on the subject's finger or any other appendage that results in valid pulse oximetry readings. Position MRI compatible surface electrodes on the subject to ensure the subject's heart rate can be continuously monitored during the scan. During the MRI scan, periodically record heart rate, and blood oxygen saturation levels. Visually examine the ECG during the MRI scan. Note any abnormalities observed in the cardiac rhythm (Refer to Life-threatening Ventricular Arrhythmia and Asystole Assessment below). After the MRI scan, remove the subject from the MRI field.

Note: Monitor subject with ECG along with the site's routine monitoring. In cases where ECG monitoring is not readily available, monitoring via pulse oximetry alone is considered acceptable.

6.4 During MRI Scan Procedures

After confirmation by the electrophysiologist or device specialist that all pre-MRI system checks (mentioned above) have been met, subjects will have the clinically indicated, non-thoracic MRI scan completed by a radiology staff member.

6.4.1 MRI Scan Parameters

When performing an MRI scan on a subject with a St. Jude Medical device system, the following scan parameters must be followed:

Table 6. MRI Scan Parameters

Scan Parameters	Setting
Scanner Type	Cylindrical bore magnet, horizontal field orientation
Magnet Strength	1.5T
Whole Body SAR (Specific Absorption Rate)	≤ 2 W/kg, Normal Operating Mode
Head SAR	≤ 3.2 W/kg
Gradient Slew Rate	≤ 200 T/m/s per axis
Spatial Gradient	≤ 30 T/m

6.4.2 Cardiac Monitoring

- During the entire MRI scan, the subject's cardiac function must be monitored by a study trained electrophysiologist, cardiologist, or Advanced Cardiac Life Support (ACLS) trained personnel capable of delivering external cardiac pacing, defibrillation and advanced cardiac life support using an ECG and/or pulse oximetry along with the site's routine monitoring. In cases where ECG monitoring is not readily available, monitoring via pulse oximetry alone is considered acceptable. Routine monitoring of the subject must also take place

Clinical Investigational Plan

to assess and/or confirm any clinically significant changes noted in the subject's oxygen saturation or heart rate, as well as any clinically significant complaints not obvious with pulse oximetry. Record these changes and complaints during the MRI scan.

- ACLS procedures must be in place to address situations where a life threatening arrhythmia and/or hemodynamic collapse occurs. The programmer must be used outside the American College of Radiology (ACR) defined Zone 4 magnet room. If the subject's hemodynamic function is compromised during the MRI scan, discontinue the MRI procedure and take proper measures to restore the subject's hemodynamic function.

6.4.3 Life-threatening Ventricular Arrhythmia and Asystole Assessment

- Monitoring of spontaneous ventricular arrhythmias and asystole must be conducted via an ECG and/or pulse oximetry during the MRI scan. Any sustained ventricular arrhythmias or asystole (see definition below) must be documented on an Adverse Event form. Non-sustained ventricular tachycardias (NSVT) or premature ventricular contractions (PVCs) do not need to be reported as an adverse event. However, if an arrhythmia reproducibly occurs (occurring more than once during the MRI scan) while the subject is actively being scanned, report the event on an Adverse Event form.

Definitions:

- **Sustained Ventricular Arrhythmia:** Heart Rate >150bpm for > 30 seconds with depolarization originating in the ventricles
- **Asystole:** A standstill > 6 seconds in electrical activity of the heart (i.e., no heart rate for 6 seconds or more)

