3.7 Steps that will be taken to control or mitigate the risks

The risks associated with MRI scanning of subjects implanted with implantable active medical devices have been identified through clinical evaluation, including an exhaustive literature search.

Risks normally associated with pacemakers, ICDs, CRTs, and transvenous leads will be minimized in the study by selecting investigators who are experienced in treating subjects implanted with these devices and are trained in the this study protocol. Subjects will be actively monitored during the MRI scan using an ECG along with the site's routine monitoring. In cases where ECG monitoring is not readily available, monitoring via pulse oximetry alone is considered acceptable. The investigator and/or other ACLS-certified personnel will be present during the MRI scan to address cases of asystole or hemodynamic collapse that may occur during the MRI scan.

Risks will also be minimized by careful assessment of each subject prior to enrollment. After enrollment, subjects in the study will be assessed as specified in this CIP to monitor the condition of the implanted system after the subject has undergone the MRI scan.

In order to limit the risk of the MRI scan for a subject with an implanted pacemaker, ICD, or CRT device system, the MRI scans will be limited to non-thoracic examinations at up to 1.5T. In addition, the following precautions will be taken based on the AHA Guidelines on Safety of Magnetic Resonance Imaging in Patients with Cardiovascular Devices¹²:

- Advanced cardiovascular life support (ACLS) trained personnel and a “crash cart”, including defibrillator, will be available throughout the procedure to address an adverse event.
- Pre-MRI scan steps outside the MR environment
- Pre-test cardiac device functions
- For pacemaker dependent subjects, reprogram to asynchronous mode
- For ICD/CRT-D, disable bradycardia and tachycardia therapy and detection and exclude pacemaker dependent patients
- The patient’s heart rhythm and vital signs should be monitored throughout the MR procedure.
- Maintain visual and voice contact with the patient throughout the procedure.
- Instruct the patient to alert the MR system operator to any unusual sensations or problems.

After the MRI scan the pacemaker, ICD, or CRT device will be interrogated to verify appropriate device function, to evaluate pacing and sensing characteristics, and to assess any adverse events.

Clinical Investigational Plan

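### Sustained ventricular arrhythmia is defined by ventricular origin, but a scan may be monitored by pulse oximetry alone, and the plan does not say how rhythm events on such scans are classified or counted

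*Combined protocol and SAP*

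**What the plan says.** Section 6.4.3 names two events that must go on an Adverse Event form: "Any sustained ventricular arrhythmias or asystole (see definition below) must be documented on an Adverse Event form". Sustained ventricular arrhythmia is "Heart Rate >150bpm for > 30 seconds with depolarization originating in the ventricles". Asystole is "A standstill > 6 seconds in electrical activity of the heart (i.e., no heart rate for 6 seconds or more".

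The same section gives the means of detection: "Monitoring of spontaneous ventricular arrhythmias and asystole must be conducted via an ECG and/or pulse oximetry during the MRI scan". The footnote to Table 4 in section 6.2 puts it differently, as ECG with a fallback: "In cases where ECG monitoring is not readily available, monitoring via pulse oximetry alone is considered acceptable". Sections 3.7 and 6.3.6 repeat the fallback. Section 6.4.2 contains both forms.

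Section 6.4.2 also requires routine monitoring "to assess and/or confirm any clinically significant changes noted in the subject's oxygen saturation or heart rate", and these changes must be recorded. Among the precautions in section 3.7 is: "For ICD/CRT-D, disable bradycardia and tachycardia therapy and detection and exclude pacemaker dependent patients".

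For analysis, section 12.1.3 promises a summary of adverse events and of MRI-related complications by device group. Section 12.8 rules out imputation. Neither gives a denominator for rhythm events. Section 14.2 has the Steering Committee follow adverse event and death rates during the study.

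**The concern.** One of the two reportable rhythm events contains a criterion, "with depolarization originating in the ventricles", that one of the two permitted instruments cannot observe. On an oximetry-only scan, a fast pulse can be seen and recorded, but the definition cannot be shown to be met.

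Oximetry-only scans should be expected. The rationale for the June 2016 amendments in Appendix B is that MRI-compatible ECG equipment is not available in every MRI center. Neither the scan data list in section 6.5.3 nor Table 4 names the monitoring method as an item to be recorded for each scan.

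What is at stake is how a low count is read. Table 1 lists induced VT/VF among the potential MRI-related events, so few or no reported ventricular arrhythmias would be taken as reassuring. Part of that reassurance could come from scans on which the event could not have been classified. Device groups or centers with different access to ECG could also show different rates for that reason alone.

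**Working it through.** **The plan's own precision figure.** Section 12.2 gives a half-width of 4.0% for the image-quality proportion with 150 scans and 95% sufficient. The exact two-sided 95% interval for 142/150 is 89.8% to 97.7%, a half-width of 3.95%, which rounds to 4.0%. It reproduces, and this point does not affect it. The plan gives no corresponding figure for rhythm events.

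**Step 1: definition against instrument.**

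| Criterion in 6.4.3 | ECG | Pulse oximetry alone |
|---|---|---|
| Rate above 150 bpm for more than 30 s | Observable | Observable as a pulse rate |
| Ventricular origin | Observable | Not observable |
| Electrical standstill | Observable | Not observable |
| No heart rate for 6 s or more | Observable | Suggested by loss of pulse; not separable from artefact or from electrical activity without a pulse |

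The gap is complete for ventricular origin and partial for asystole. The asystole definition is also inconsistent at its boundary: its first half needs more than 6 seconds, while its gloss accepts exactly 6.

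**Step 2: other records of rhythm.** Under the section 3.7 precautions, ICD/CRT-D detection is off for the scan. Section 6.5.1 requires interrogation, underlying rhythm, battery, capture, sensing and impedance afterwards. It does not name retrieval of rhythm episodes from the scan period.

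**Step 3: direction of the error.** Let π be the true rate of sustained ventricular arrhythmia during scanning, f the share of scans with ECG, and d the chance that an event is classified under oximetry relative to ECG. With all scans in the denominator, the expected reported rate is

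π × [f + (1 − f) × d].

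At d = 1 there is no understatement. At d = 0 the reported rate is f × π: 70% of the true rate if 30% of scans are oximetry-only, and half of it if 50% are. Two device groups with the same π but f = 1 and f = 0.5 would then differ by a factor of 1/0.5 = 2.

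**Step 4: size in the extreme case.** Take zero events in a device group of 150 scans (section 12.2) and d = 0. The one-sided 95% exact upper bound on n informative scans is U = 1 − 0.05^(1/n). The oximetry-only share is an assumption, because the documents give none.

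| Oximetry-only share (assumed) | Informative scans | U |
|---|---|---|
| 0% | 150 | 1 − 0.05^(1/150) = 1.98% |
| 30% | 150 × 0.70 = 105 | 1 − 0.05^(1/105) = 2.81% |
| 50% | 150 × 0.50 = 75 | 1 − 0.05^(1/75) = 3.92% |

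Any d above zero places the answer between the first row and the row for the relevant share.

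**The case against.** The strongest reply is that reduced certainty about rhythm is not the same as no detection. Section 6.4.2 requires an electrophysiologist, cardiologist or ACLS-trained person to monitor throughout. Changes in heart rate and complaints must be recorded, and the Clinical Events Committee adjudicates from case report forms, medical records and clinical judgement (section 14.1). Section 6.5.4 also calls for upload of device session records from before and after the scan. A sustained fast pulse or a lost pulse would probably be noted. This stands, and it is why the bounds above are an extreme case. It does not close the gap: the committee cannot establish ventricular origin if no record shows it, and the plan offers no category for that outcome.

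A reader might infer that the plan counts unascertainable events as non-events. The documents do not say so. Section 12.1.3 states no denominator, and a no-imputation rule does not turn a missing classification into an absence. Undercounting follows only if all scanned subjects are used as the denominator.

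A reader might also infer that asystole cannot be identified at all under oximetry. The heart-rate gloss in its definition does not support that.

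The case report forms are held separately (Appendix G), and the list in section 6.5.3 is expressly not exhaustive, so the monitoring method may already be collected. Finally, the study has no hypothesis, pass/fail criterion or planned subgroup analysis, and its primary endpoints concern image quality. That limits the importance of the point without answering it.

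**Conclusion.** The point holds in a limited form. The definition of sustained ventricular arrhythmia depends on an electrical feature that a permitted monitoring method cannot show, and the plan text neither lists the method as a data item nor says how a rhythm event seen only on oximetry is classified. If all scanned subjects form the denominator, the scan-period ventricular arrhythmia rate may be understated and may differ between device groups because of ECG availability. Asystole is affected only in part.

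The size is unknown because the oximetry-only share is unknown. The movement from 1.98% to 2.81% or 3.92% rests on three assumptions: zero events, a 30% or 50% oximetry-only share, and no detection under oximetry. It would be wrong to read 105 or 75 as the one correct denominator for every rhythm event, or to read these bounds as replacing a planned safety bound, since the plan has none. Nor does the point show that the oximetry fallback itself is wrong. No primary analysis or sample size changes. This is an inexpensive improvement to the safety reporting.

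**What to change.** 1. Reconcile the definitions in section 6.4.3 with the monitoring text, leaving patient monitoring unchanged. Two inconsistencies need attention: the either-or-both wording in 6.4.2 and 6.4.3 against ECG with an oximetry fallback in 3.7, 6.3.6, 6.4.2 and Table 4; and more than 6 seconds against 6 seconds or more for asystole. Which clinical wording is right is for the sponsor and its clinical advisers to decide.
2. Record the monitoring method for each scan (ECG, or pulse oximetry alone) on the MRI Scan CRF, if it is not already collected. This should be done during the study, because the method may not be recoverable later.
3. In section 12.1.3, report scan-period ventricular arrhythmia and asystole by monitoring method within each device group. Use ECG-monitored scans as the denominator for ventricular arrhythmia, show oximetry-only scans on a separate line, and add an indeterminate-rhythm category for events seen only on oximetry.

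The cost is at most one CRF field, plus a few table lines and a short wording change. Any upper bound that is reported for ventricular arrhythmia will be somewhat less favourable.
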